### 7.3 Exploratory Efficacy Endpoints

Exploratory efficacy endpoints include:

- Proportion of subjects in the MITT and PP Populations with a diagnosis of HABP at >48 hours post-extubation up to but not including Day 22 in extubated subjects;
- Proportion of subjects in the MITT and PP Populations with development of VABP up to but not including Day 22;
- Incidence of all bacterial pneumonias in the MITT, ITT, and PP Populations;
- Incidence of other non-*S. aureus* pneumonias up to but not including Day 22 in the MITT, ITT, and PP Populations; and
- Incidence of other *S. aureus* infections acquired following study drug administration up to but not including Day 22 in the MITT, ITT, and PP Populations.

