### 2.2. Additional Objectives

Additional objectives of this sub-study are to compare ASN100 versus placebo (added to standard of care) with regard to the following:

- The duration of mechanical ventilation post-treatment;
- The resolution time for *S. aureus* pneumonia, all bacterial pneumonias, and non-*S. aureus* bacterial pneumonia;
- The length of stay in the intensive care unit (ICU) and length of hospital stay post-treatment;
- 28-day all-cause mortality;
- The incidence of other *S. aureus*-associated infections which occur after dosing up to but not including Day 22; and
- Serum pharmacokinetics (PK) (i.e., maximum serum concentration [ $C_{max}$ ], time to maximum serum concentration [ $T_{max}$ ], area under the serum concentration-time curve [AUC], and terminal elimination half-life [ $t_{1/2}$ ]) of ASN-1 and ASN-2 in mechanically ventilated subjects heavily colonized with *S. aureus* who developed pneumonia;
- ASN-1 and ASN-2 levels in bronchoalveolar lavage (BAL) fluid and calculate a blood to epithelial lining fluid (ELF) ratio in those subjects who undergo BAL as part of their microbiological evaluation of their pneumonia or as part of their standard of care;
- Immunogenicity (development of anti-drug antibodies) of a single dose of ASN100.

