An adequate respiratory sample (defined in the primary study) to determine the microbiological etiology of the pneumonia is to be collected within 36 hours of randomization, although all attempts should be made to obtain the specimen as close as possible to when the diagnosis of pneumonia is made. Note: Any time a BAL/non-bronchoscopic BAL or protected specimen brush (PSB) is performed to collect a respiratory microbiological sample, then a PK sample should also be collected to determine ASN-1 and ASN-2 levels to derive blood to ELF ratio, and to measure *S. aureus* toxins.

While hospitalized, randomized subjects will be monitored daily for up to 21 days for pneumonia resolution or recurrence, and the occurrence of other *S. aureus*-associated infections. If a subject's clinical symptoms of pneumonia improve such that no further antibiotic therapy is required, or if the pneumonia persists requiring a change in antibiotic therapy, then all attempts will be made to collect an adequate respiratory specimen.

All randomized subjects will undergo a study visit on Day 22 (+2 days) for assessment of pneumonia. An adequate respiratory specimen should be obtained from subjects who remain ventilated and non-ventilated subjects who are able to produce sputum.

A Follow-Up Visit will occur on Day 28 (+2 days) to assess mortality. This visit may be conducted via telephone if the subject is no longer hospitalized.

For subjects who remain hospitalized between Days 40 and 90 at the institution where they receive study treatment, the Follow-Up Visit will be performed on the day of discharge.

All randomized subjects will return for a Safety Visit on Day 90 ( $\pm 7$  days) (if the subject is unable to return to the site, this visit may be conducted by telephone). Subjects who discontinue the study prior to Day 22 will undergo an Early Termination Visit. The end of the study will occur upon completion of the last study visit (e.g., Day 90) visit by the last subject.

Safety assessments for this study will include adverse event (AE) monitoring, clinical laboratory assessments (including chemistry, hematology, coagulation, and urinalysis), physical examinations, vital sign measurements, 12-lead electrocardiograms (ECGs), chest X-rays and/or thoracic computed tomography (CT) scans, and the determination of the presence of ASN-1 and ASN-2 anti-drug antibodies (ADAs). Additional safety assessments may be performed throughout the duration of the study if clinically indicated.

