### 7.2. Additional Efficacy Endpoints

- The time to resolution of *S. aureus* pneumonia in the modified intent-to-treat (MITT), mMITT, and expanded microbiologically evaluable modified intent-to-treat (E-mMITT) Populations;
- The time to resolution of all bacterial pneumonia in the MITT and mMITT Populations;
- The time to resolution of non-*S. aureus* pneumonia in the MITT and mMITT Populations;
- Duration of mechanical ventilation during the first 21 days post-randomization for subjects in the MITT, mMITT, and E-mMITT Populations;
- Length of ICU and hospital stay during the first 21 days post-randomization for subjects in the MITT, mMITT, and E-mMITT Populations;
- $C_{max}$ ,  $T_{max}$ , AUC, and  $t_{1/2}$  of ASN-1 and ASN-2 in serum following a single dose of ASN100 in the pharmacokinetic (PK) Population;
- 28-day all-cause mortality in the MITT, mMITT, and E-mMITT Populations;
- Development of ADAs to a single dose of ASN100;
- ASN-1 and ASN-2 levels in BAL fluid and blood to ELF ratio; and
- Incidence of other non-pulmonary *S. aureus* infections acquired following study drug administration up to the final study visit (e.g., Day 90, Early Termination, etc.) in the mMITT and E-mMITT Populations.

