## 10. APPENDICES

### 10.1. Schedule of Procedures for Sub-Study

Study Period	Random-ization	Treatment	Monitoring Period			Follow-Up Period			ET
Study Day	Day 1 Pre-dose	Day 1	Day 2/3 j (BAL PK Sub-study)	Days 2 to 21 k	Day 22 (+2 days)	Day 28 (+2 days) l	Days 40 to 89 m	Day 90 (±7 days) Safety Visit n	Unsched o
Study Procedures									
Inclusion/exclusion criteria	X p								
Medical history a	X								
Antibiotic/medication history a	X								
Physical examination b	X			X	X		X	X	X
Vital signs c	X	X	X	X	X		X	X	X
Pregnancy test d	X				X				X
Clinical lab assessments e	X			X	X				X v
Urinalysis	X			X q	X				X v
Procalcitonin (central lab)	X				X				X
Ventilator device status	X	X	X	X	X	X	X	X	X
Chest X-ray/thoracic CT scan	X		X	X r	X				X r
Nasal swab for culture	X								
Collection/culture of respiratory microbiological specimens f		X		X s	X t				X t
Collection/culture of additional microbiological specimens g				X	X				X
Clinical assessment of signs/symptoms of pneumonia	X	X	X	X	X				X
Other S. aureus infection assessment	X	X	X	X	X				X
Randomization	X								
Blood collection for ADA and anti- S. aureus toxin antibodies	X			X u	X		X	X	X
12-lead ECG	X				X		X	X	X
Survival and discharge disposition					X	X	X	X	X

Study Period	Random-ization	Treatment	Monitoring Period			Follow-Up Period			ET
	Day 1 Pre-dose		Day 1	Day 2/3 i (BAL PK Sub-study)	Days 2 to 21 k	Day 22 (+2 days)	Day 28 (+2 days) l	Days 40 to 89 m	Day 90 (±7 days) Safety Visit n
Study Procedures									
Study drug administration h		X							
BAL for PK (Optional)			X						
Blood collection for PK sampling and anti- S. aureus toxin antibodies		X v	X w	X x	X x		X x	X	X
Track days on ventilator from randomization		X	X	X	X		X	X	X
Track days in ICU (or other observation area)		X	X	X	X		X	X	X
Concomitant medications i	X	X	X	X	X		X	X	X
Adverse event assessment	X	X	X	X	X		X	X	X

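### Appendix C: the objective for other S. aureus infections stops before Day 22, but its endpoint runs to each subject's final visit, beyond the scheduled infection assessments

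*Protocol*

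**What the plan says.** All references are to Protocol Appendix C unless stated.

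- **Objective (2.2).** The additional objectives are "to compare ASN100 versus placebo (added to standard of care) with regard to the following". The list includes other S. aureus-associated infections "which occur after dosing up to but not including Day 22".
- **Endpoint (7.2).** The last additional endpoint is an incidence, limited to infections with S. aureus that are non-pulmonary. Its window is given as "acquired following study drug administration up to the final study visit (e.g., Day 90, Early Termination, etc". It is to be reported for two populations, mMITT and E-mMITT.
- **Monitoring (Section 3).** The design text reads "While hospitalized, randomized subjects will be monitored daily for up to 21 days for pneumonia resolution or recurrence, and the occurrence of other" (the sentence then names the S. aureus-associated infections).
- **Schedule (10.1).** The row "Other S. aureus infection assessment" is marked at Day 1 pre-dose, Day 1, Day 2/3, Days 2 to 21, Day 22 and Early Termination. It is blank at Day 28, Days 40 to 89 and Day 90. The row for additional microbiological specimens likewise has no mark after Day 22 other than Early Termination, and the footnotes confine that visit to withdrawals before Day 22.
- **Analysis (9.3).** Endpoints not named there are summarized by arm. Nothing is said about death, withdrawal or differing follow-up. The SAP does not cover this treatment sub-study.
- **Main study (Protocol 7.3).** The corresponding endpoint covers S. aureus "infections acquired following study drug administration up to but not including Day 22".

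**The concern.** The objective and the only endpoint that serves it cover different periods and use different terms for the infections counted. One analyst working from 2.2 and another working from 7.2 would produce different tables, and nothing in 9.3 or the SAP says which is meant.

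The longer window also brings two weaknesses that the shorter one largely avoids. Most of it lies after the last scheduled infection assessment. It also closes on a date specific to each subject, so a plain incidence counts infections over follow-up that can run from a few days to about three months. Mortality is itself an endpoint of the sub-study. If ASN100 improved survival or retention, the treated arm would have more time in which to record an infection, and its incidence could look higher with no effect of the drug on infection.

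**Working it through.** The plan states no event rate, power or sample size for this endpoint, so there is no figure to reproduce.

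**1. Windows side by side**

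| Source | Window for other S. aureus infections |
|---|---|
| App. C 2.2, objective | dosing to before Day 22 |
| App. C 3, monitoring | daily for up to 21 days, while hospitalized |
| App. C 10.1, schedule | through Day 22, or Early Termination |
| Protocol 7.3, main study | dosing to before Day 22 |
| App. C 7.2, endpoint | dosing to own final visit, for example Day 90 |

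The endpoint is the only entry that goes past Day 22. The sub-study's primary endpoint (7.1) also stops before Day 22.

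**2. Share of the endpoint window after the last scheduled assessment**

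Share = (final day − last assessment day) / final day.

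- Final visit Day 90, last assessment Day 22: (90 − 22)/90 = 68/90 = 76%.
- Lowest over the visit windows (final Day 83, last assessment Day 24): 59/83 = 71%.
- Highest (final Day 97, last assessment Day 21): 76/97 = 78%.

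**3. Direction of the follow-up effect**

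The documents give no infection, death or withdrawal rates for the sub-study, so the following is an illustration on assumed rates, not an estimate. Assume constant daily hazards, λ for infection (the same in both arms) and μ for death or withdrawal. The proportion with a recorded infection by day t is

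λ/(λ+μ) × [1 − exp(−(λ+μ)t)].

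Assume an infection risk by Day 21, in the absence of loss, of 5%, 10% or 20%, with λ = −ln(1 − risk)/21. Set μ from an assumed 28-day loss as μ = −ln(1 − loss)/28.

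For 10% risk and 20% v 30% loss (ASN100 v placebo), λ = 0.00502, μ = 0.00797 and 0.01274. At t = 90 this gives 26.6% v 22.5%, and at t = 21 it gives 9.2% v 8.8%.

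| 28-day loss, ASN100 v placebo | Incidence to Day 21 (10% risk) | Incidence to Day 90 (10% risk) | Ratio to Day 21, all three risks | Ratio to Day 90, all three risks |
|---|---|---|---|---|
| 30% v 30% | 8.8% v 8.8% | 22.5% v 22.5% | 1.00 | 1.00 |
| 20% v 30% | 9.2% v 8.8% | 26.6% v 22.5% | 1.05 | 1.16 to 1.19 |
| 15% v 35% | 9.4% v 8.6% | 28.9% v 20.7% | 1.10 | 1.35 to 1.42 |

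With equal loss there is no distortion in either window. With unequal loss the longer window enlarges it, and the shorter one reduces it without removing it. At about 25 subjects per arm (50/2), the middle row's Day 90 difference of 4.1 percentage points is about one subject (0.041 × 25 = 1.0).

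**The case against.** **Late infections are not lost.** A reader might infer from the blank schedule cells that infections after Day 22 go unobserved. The documents do not support that. Adverse events are recorded until participation ends (Protocol 9.1), serious ones are reported to the Day 90 visit (9.3), and the sub-study schedule marks adverse events at Days 40 to 89 and Day 90. Culture results from standard of care during the study go into the case report form (Appendix C 7.3.1). The exception that keeps efficacy failures out of adverse event reporting concerns pneumonia, so a late non-pulmonary infection is reportable. This stands. The 76% is time without a dedicated assessment, not time without data.

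**Unequal follow-up between arms is conditional.** A reader might also infer that the arms will be compared over unequal follow-up. Follow-up differs between subjects by definition, but between arms only if death or withdrawal differs, and no sub-study rates are given. This stands too. Constant risk to Day 90 is also a generous assumption once subjects leave the ICU or hospital.

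**The longer window may be deliberate.** Its examples are explicit, and Appendix C Section 6 allows minor modifications for the treatment aims. That is possible, but the objective and schedule were not changed to match, so the text still needs reconciling. The Day 90 data contain the earlier period, so nothing needed for the objective would be missing. That makes the repair cheap; it does not settle which table is planned.

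**A Day 22 window is not clean either.** It also ends early at death or withdrawal, and daily monitoring applies only in hospital. This stands as a limit of the fix.

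**Conclusion.** The point holds as an inconsistency between objective and endpoint, at low severity. Appendix C 2.2 and 7.2 give different windows and different infection scopes for one comparison, and only the objective's window matches the monitoring text, the schedule and the main study. With a Day 90 final visit, 68 of 90 days (76%; 71% to 78% over the visit windows) rest on passive capture. This follows from the documents alone.

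The absence of a follow-up rule in 9.3 is a vulnerability, not a demonstrated bias. It matters only if death or withdrawal differs by arm, and its size cannot be given from the documents. The ratios in the working depend wholly on assumed constant rates and show direction only. A reader might take them as a forecast that ASN100 will appear to raise infections; nothing in the plan supports that.

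The consequence is confined to one descriptive additional endpoint, with no named test, in a sub-study of about 50 subjects and possibly fewer in the mMITT and E-mMITT Populations. The sub-study primary endpoint and the main study are untouched.

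**What to change.** Before unblinding:

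1. In Appendix C 7.2, end the comparative window for this endpoint where the objective ends it: infections "which occur after dosing up to but not including Day 22".
2. Use one infection scope in 2.2 and 7.2, either S. aureus-associated or non-pulmonary, and state it in both places.
3. Report S. aureus infections from Day 22 to the final visit as a listing by arm, drawn from adverse event and culture data, without a comparative incidence.

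The cost is a short text edit in two sections and one listing. No visit, sample or data item is added and no data are discarded. The downside is that late infections leave the between-arm comparison, and some distortion from death or withdrawal before Day 22 remains.

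If the sponsor does want a comparison to Day 90, the consistent alternative is to amend the objective, schedule the infection assessment through Day 90, and specify a time-to-event analysis with death as a competing event. That costs more and is hard to justify for an additional endpoint of this size.

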### 7.3. Microbiological and Clinical Assessments

#### 7.3.1 Microbiological Assessment

In the primary study, ETA specimens will be collected for culture during the Screening/Enrollment Period to determine the degree of *S. aureus* colonization. Additional respiratory specimens may be collected for culture throughout the Monitoring Period or at Early Termination (if applicable) if clinically indicated according to standard of care.

If, as part of routine standard of care, additional respiratory and/or other microbiological specimens are collected for culture during the study, results will be documented within the electronic case report form. As described within the study laboratory manual, bacterial isolates recovered from these specimens that are deemed pathogens by the Investigator (if retained and available at the study site local microbiology laboratory) will be sent to a central microbiology laboratory for confirmation of pathogen identification (all isolates) and susceptibility testing (*S. aureus* isolates only).

For a Sponsor diagnosis of *S. aureus* pneumonia, an adequate respiratory specimen culture that is positive for *S. aureus* must be obtained within 36 hours from randomization.

- For intubated subjects, a respiratory specimen obtained by BAL, non-bronchoscopic BAL, or PSB will be considered an adequate respiratory specimen;
- For extubated subjects, an adequate expectorated/induced sputum specimen is defined as <10 squamous epithelial cells and >25 PMNs/100× field; and
- Adequate respiratory specimens will undergo either semi-quantitative or quantitative culture in accordance with the local laboratory standard procedure. For each subject, the sampling and testing method should be consistent for microbiological diagnosis of both pneumonia and its resolution.

### 7.3.2 Assessment of Clinical Signs/Symptoms and Pneumonia Progression Status

Subjects will be assessed daily throughout the Monitoring Period for the following clinical signs and symptoms and pneumonia progression status:

#### Clinical Signs and Symptoms and Pneumonia Progression Status

Mechanically Ventilated Subjects	Non-Mechanically Ventilated Subjects
Cough	Cough
Rales	Rales
Dullness on percussion *	Dullness on percussion *
Bronchial breath sounds	Bronchial breath sounds
Egophony*	Egophony*
Need for suctioning	Dyspnea
Need for ventilator support	Tachypnea
Fever ≥38°C (≥100.4°F)	Respiratory rate
Presence of purulent secretions	Hypoxemia
PaO 2 (if measured)	Fever ≥38°C (≥100.4°F)
FiO 2 (most representative setting)	Supplemental oxygen (i.e., nasal canula 2L, face mask at 30% O 2 )
PEEP (most representative setting)	Presence of purulent secretions

FiO2 = fraction of inspired oxygen; PaO2 = partial pressure of oxygen in arterial blood; PEEP = Positive end-expiratory pressure

\*If routinely performed.

### 7.3.3 Evaluation of Pneumonia Outcomes

#### 7.3.3.1. Clinical Outcomes of Pneumonia According to Investigator

In addition to the daily assessment of respiratory signs and symptoms, the Investigator will make a determination of pneumonia resolution if the subject meets all four of the following criteria:

- Complete resolution of all or most of the pneumonia clinical signs and symptoms;
- No new signs, symptoms, or complications of pneumonia;
- No additional antibiotic therapy administered for pneumonia; and
- Subject is alive.

### 7.3.3.2. Clinical Outcomes at Day 22 (Test of Cure)

Clinical outcome will be assessed by the Sponsor as cured, failure, or indeterminate using the criteria below. The classifications will be determined at Study Day 22 based on data collected and reported by the Investigator during the monitoring period.

#### Cured

To be classified as cured, subjects must meet all of the following criteria:

1. Alive
2. Resolution of signs and symptoms of infection or significant improvement of the index infection, including all of the following:
  - Improvement in signs and symptoms since diagnosis of pneumonia;
  - Improvement in oxygenation, as defined by any of the following:
    - Extubation (or removal of tracheostomy tube);
    - Improvement in  $\text{PaO}_2:\text{FiO}_2$  by  $\geq 20$  mmHg [ $\geq 2.7$  kPa]; or
    - Reduction in PEEP  $\geq 2$  cm for at least 2 consecutive days.(Note: Failure of extubation should not be considered a clinical failure if it is due to reasons other than pneumonia; the reason for failure of extubation should be documented.)
  - Absence of fever (core temperature of  $>38.0^\circ\text{C}$  [ $>100.4^\circ\text{F}$ ]) or hypothermia ( $<35^\circ\text{C}$  [ $<95^\circ\text{F}$ ]);
  - Absence of purulent sputum or other deep respiratory specimen; and
  - A 25% or more decrease in WBC count from the peak value associated with the diagnosis of pneumonia if the WBC was greater than  $11,000/\text{mm}^3$
3. No requirement for new or additional antimicrobial therapy for treatment of pneumonia and did not require antibiotic therapy beyond Study Day 14

#### Failure

Subjects meeting either of the following criteria will be classified as failures:

1. Subject fails to meet any of the criteria for cure (above) or
2. Subject dies of pneumonia  $>48$  hours post-treatment with study medication

#### Indeterminate

Subjects meeting any the following criteria will be classified as indeterminate:

1. Subjects lost to follow-up;
2. Subjects for whom data are unavailable to allow for a determination of clinical cure or failure;
3. Subjects who die within the first 48 hours; or

4. Subjects who change antibiotic therapy within the first 48 hours based on insufficient therapeutic effect.

### 7.3.3.3. Microbiological Outcomes at Day 22 (Test of Cure)

Eradication (documented or presumed) of the baseline pathogen(s) will be considered microbiological success while any new pathogen or persistence (documented or presumed) will be considered microbiological failure. Specific microbiological outcomes definitions are as follows:

Eradication:	Absence of the baseline pathogen in an adequate post-baseline respiratory specimen.
Presumed Eradication:	Absence of an adequate post-baseline respiratory specimen to culture in a subject deemed a clinical cure.
Persistence:	Presence of the baseline pathogen in an adequate post-baseline respiratory specimen.
Presumed Persistence:	Absence of an adequate post-baseline respiratory specimen to culture in a subject deemed a clinical failure.
Indeterminate:	Non-qualifying growth from the baseline respiratory culture or any confounding factors (e.g., early discontinuation from study medication) that prevent the assignment of an appropriate microbiologic outcome.
Recurrence or Relapse:	Isolation of a S. aureus strain from an adequate post-baseline respiratory specimen after documented eradication.
Emergent Infections or Superinfection:	Isolation of a different pathogen, other than a baseline pathogen, from an adequate post-baseline respiratory specimen obtained in a subject with signs and symptoms of infection, while the subject is still on antibiotic therapy for the original infection.
New Infection:	Isolation of a different pathogen, other than the baseline pathogen, from a culture obtained after completion of antibiotic therapy in a subject with signs and symptoms of infection.

